### **8.6.2. Handling the IMP/Devices at the Investigational Center**

The Investigator is responsible for retaining the product in question in a location separate from the Investigator's clinical trial supplies. The Sponsor may request that the Investigator return the product for further evaluation and/or analysis. If this is necessary, the clinical trial monitor or designee will provide the information needed for returning the IMP (and/or PFS).

If it is determined that the investigational center must return all IMP (and/or PFS), the Sponsor will provide the information needed to handle the return.

The integrity of the randomization code and corresponding blinded clinical supplies will be maintained whenever possible. A serious adverse event or the potential for a product quality problem existing beyond the scope of the complaint may be a reason to unblind the clinical supplies for an affected participant.

### **8.6.3. Product Complaint Associated with Adverse Events or Serious Adverse Events**

If there is an adverse event or serious adverse event due to product complaint, the protocol should be followed for recording and reporting of the adverse event or serious adverse event (Section 8.4.2 to Section 8.4.7).

### **8.6.4. Product Complaint Information Needed from the Investigational Center**

In the event that the Product Complaint Form cannot be completed, the Investigator will provide the following information, as available:

- investigational center number and Principal Investigator name
- name, phone number, and address of the source of the complaint
- clinical protocol number
- participant identifier (participant trial number) and corresponding visit numbers, if applicable
- product name and strength for open-label trials
- participant number, bottle, and kit numbers (if applicable) for double-blind or open-label trials
- product available for return Yes/No
- product was taken or used according to protocol Yes/No
- description or nature of complaint
- associated serious adverse event Yes/No
- clinical supplies unblinded (for blinded trials) Yes/No
- date and name of person receiving the complaint

### **8.6.5. Device Deficiency that Could Have Led to Serious Adverse Event**

Device deficiencies that could have led to serious adverse events are defined as deficiencies that might have led to a serious adverse device effect if (see Figure 2):

- suitable action had not been taken (or)
- intervention had not been made (or)
- if circumstances had been less fortunate

These device deficiencies shall be reported to the IRB/IEC by the Investigator and to the regulatory authorities by the Sponsor or manufacturer (for devices not manufactured by the Sponsor) according to the national and local regulations.

The Investigator will record in the source documentation a description of the complaint, the initial determination whether the device deficiency could have led to a serious adverse event, and any actions taken to resolve the complaint and to preserve the safety of the participant.

The Investigator should use [Table 4](#), and [Table 5](#) to help make an initial determination whether the device deficiency could have led to a serious adverse event and include this assessment in the Product Complaint Form.

**Table 4: Anticipated Use-Related Deficiencies and Their Potential Hazards and Serious Harms**

Use step	Use error	Potential hazard situation	Potential harm
Obtain sharps container and dispose of the device	Syringe not disposed of correctly after use	Needle stick third party	Third party death
Check that IMP name appears on device	Failure to check IMP information.	Incorrect medicament injected	Participant death
Store carton within the refrigerator	Fail to store product correctly	Participant exposed to toxic substance due to degraded drug	Permanent impairment or life threatening injury
Inspect the device	Fail to perceive or recognize a need to visually inspect the device; Incorrect mental model of what would be considered to constitute 'damage'; Expiration date check not completed; Misread the expiration date; etc.	Inject degraded or expired IMP	Toxicity – Permanent impairment or life threatening injury

IMP=investigational new drug.

**Table 5: Anticipated Design-Related Deficiencies and Their Potential Hazards and Serious Harms**

Device component	Failure mode	Potential hazard situation	Potential harm
PFS components (Barrel-needle, RNS, plunger rod, backstop, syringe label)	PFS components are not biocompatible	User is exposed to an irritant, a toxic substance and/or a sensitizer	Toxicity - Permanent impairment or life threatening injury
PFS components (Barrel-needle, RNS, plunger rod, backstop, syringe label)	PFS components are not compatible with drug	User injects degraded drug. Participant exposed to a toxic substance	Toxicity - Permanent impairment or life threatening injury
RNS and syringe barrel with needle	RNS is smaller than needle leaving needle exposed	Needle sterility compromised. Drug is contaminated	Infection – Permanent impairment or life threatening injury
RNS and syringe barrel with needle	Too much radial clearance between needle and inside of RNS. RNS comes off easily.	Needle sterility compromised. Drug is contaminated.	Infection – Permanent impairment or life threatening injury
Syringe barrel	Barrel view is occluded	User is exposed to toxic substance	Toxicity - Permanent impairment or life threatening injury

Device component	Failure mode	Potential hazard situation	Potential harm
Syringe label	Label is illegible	User is exposed to toxic substance	Toxicity - Permanent impairment or life threatening injury
Syringe label	Misinformation or label is incorrect.	User is exposed to toxic substance or degraded drug	Permanent impairment or life threatening injury
Product IFU	Misinformation or missing information. IFU is incorrect or incomplete.	User is exposed to toxic substance or degraded drug	Permanent impairment or life threatening injury

IFU=instructions for use; PFS=pre-filled syringe; RNS=rigid needle shield.

## 8.7. Pharmacokinetics

Sampling for pharmacokinetics will be sparse. Thus, the test IMP pharmacokinetic samples will be analyzed using a population pharmacokinetic approach and will be reported separately from the clinical study report (CSR).

Samples from participants who receive test IMP will be analyzed for fremanezumab using a validated method. Samples from participants who receive placebo IMP will not be analyzed.

### 8.7.1. Pharmacokinetic Sampling

Blood samples (2 mL) will be collected via venipuncture or indwelling catheter at the time points detailed in [Table 1](#) for plasma concentration measurements of fremanezumab.

The dates and times of IMP administration and each pharmacokinetic sample will be recorded on the source documentation and transcribed onto the CRF.

Details on sample handling, storage, shipment, and analysis are given in the Laboratory Manual. Assessment of ECG should precede pharmacokinetic blood sampling (see [Table 1](#)).

## 8.8. Pharmacodynamics

Pharmacodynamic parameters are not evaluated in this trial.

## 8.9. Genetics

Genetic parameters are not evaluated in this trial.

## 8.10. Biomarkers

Biomarkers are not evaluated in this trial.

## 8.11. Immunogenicity Assessments

Samples from participants who receive test IMP will be analyzed for ADA using a validated method. Samples from participants who receive placebo IMP will not be analyzed.

Blood samples (4 mL) will be collected via venipuncture or indwelling catheter at the time points detailed in [Table 1](#) for immunogenicity testing.

Details on sample handling, storage, shipment, and analysis are given in the Laboratory Manual.

## 8.12. Medical Resource Utilization and Health Economics

Health economics or medical resource utilization and health economics parameters are not evaluated in this trial.

## 8.13. Total Blood Volume

The total blood volume to be collected for each participant in this trial is approximately 48 mL, as summarized in [Table 6](#).

**Table 6: Total Blood Volumes to be Collected from an Individual Trial Participant**

Type of samples	Volume per sample (mL)	Total number of samples	Total volume (mL)
Clinical laboratory (serum chemistry, including $\beta$ -HCG test, hematology, coagulation)	10	3	30
Pharmacokinetics	2	3	6
ADA	4	3	12
Total			48

ADA=antidrug antibody;  $\beta$ -HCG=beta-human chorionic gonadotropin.

## 9. STATISTICAL CONSIDERATIONS

This section describes the statistical analysis as foreseen at the time of planning the trial. Changes, additions, and further details about the analyses will be described in the Statistical Analysis Plan. After finalization of the Statistical Analysis Plan, any additional analyses or changes to analyses that may be required will be fully disclosed in the CSR.

The analysis will be conducted on all participant data at the time the trial ends.

### 9.1. Analysis Sets

#### 9.1.1. Safety Analysis Set

The safety analysis set will include all randomized participants who receive at least 1 dose of IMP.

In the safety analysis set, treatment will be assigned based on the treatment participants actually received, regardless of the treatment to which they were randomized.

#### 9.1.2. Intent-to-Treat Analysis Set

The intent-to-treat (ITT) analysis set will include all randomized participants.

In the ITT analysis set, treatment will be assigned based on the treatment to which participants were randomized, regardless of which treatment they actually received.

#### 9.1.3. Full Analysis Set

The full analysis set (FAS) will include all participants in the ITT population who receive at least 1 dose of IMP and have at least 10 days of diary entries postbaseline for efficacy assessments on the primary endpoint.

#### 9.1.4. Per-Protocol Analysis Set

The per-protocol analysis set will consist of all participants in the FAS who have completed the trial without any important deviations, such as important inclusion/exclusion criteria deviations, important deviations or omissions of the IMP administration, or unexpected drug concentration findings, and who have at least 75% diary compliance after the start of treatment.

#### 9.1.5. Trial Population

The ITT analysis set (Section 9.1.2) will be used for all trial population summaries unless otherwise specified. Summaries will be presented by treatment group and for all participants.

##### 9.1.5.1. Participant Disposition

Data from participants screened; participants screened but not randomized and reason not randomized; participants who are randomized; participants randomized but not treated; participants in the ITT, safety, and other analysis sets; participants who complete the trial; and participants who withdraw from the trial will be summarized using descriptive statistics. Data from participants who withdraw from the trial will also be summarized by reason for withdrawal using descriptive statistics.

### **9.1.5.2. Demographic and Baseline Characteristics**

Participants demographic and baseline characteristics, including medical history, prior medications, and 12-lead ECG findings, will be summarized by treatment group using descriptive statistics. For continuous variables, descriptive statistics (number [n], mean, standard deviation [SD], median, minimum, and maximum) will be provided. For categorical variables, participant counts and percentages will be provided. Categories for missing data will be presented, if necessary.

Treatment groups will be compared for all continuous variables, using an analysis of variance with treatment group as factors. The categorical variables of participant sex and race will be summarized using descriptive statistics for each variable category. Missing categories will be presented, if necessary. Treatment groups will be compared for all categorical variables using a Pearson's chi square (or Fisher's exact test if cell sizes are too small).

## **9.2. Analyses Supporting Primary Objective(s)**

For the purpose of this trial, a migraine day will be defined as a calendar day where the participant reports either of the following:

- headache pain that lasts  $\geq 2$  hours and is accompanied by  $\geq 1$  migraine symptom(s)
- the patient used acute migraine-specific medication (triptans or ergots) to treat a headache of any severity or duration

The detailed algorithm for deriving migraine days will be described in the statistical analysis plan.

### **9.2.1. Primary Endpoint**

The primary efficacy endpoint is the mean change from baseline (28-day baseline period) in the monthly average number of migraine days during the 12-week period after the first dose of IMP.

#### **9.2.1.1. Estimand for the Primary Endpoint**

The primary estimand for this trial is the difference in means between the fremanezumab group and the placebo group in the target population who have received at least 1 dose of IMP and have at least 10 days of eDiary efficacy data for the mean change from baseline in the monthly average number of migraine days during the 12-week period after the first dose of IMP as if there were no intercurrent events. Data collected after treatment discontinuation or prohibited therapy will not be used for assessing the primary estimand.

### **9.2.2. Secondary Endpoints**

The secondary efficacy endpoints are as follows:

- mean change from baseline (28-day baseline period) in monthly average number of headache days of at least moderate severity during the 12-week period after the first dose of IMP
- proportion of participants reaching at least 50% reduction in the monthly average number of migraine days during the 12-week period after the first dose of IMP

- mean change from baseline (28-day baseline period) in the monthly average number of days of use of any acute headache medications during the 12-week period after the first dose of IMP
- mean change from baseline (day 1) in migraine-related disability score, as measured by the PedMIDAS questionnaire, at 12 weeks after administration of the first dose of IMP
- mean change from baseline (day 1) in quality of life, as measured by the PedsQL, at 12 weeks after administration of the first dose of IMP
- proportion of participants developing ADAs throughout the trial. The impact of ADAs on safety and efficacy will be analyzed if the number of ADA-positive participants allows

#### 9.2.3. Exploratory/Other Endpoints

#### **9.2.4. Planned Method of Analysis**

The FAS (see Section 9.1.3) will be used for all efficacy analyses. Summaries will be presented by treatment group.

##### **9.2.4.1. Primary Efficacy Analysis**

The primary efficacy endpoint, the mean change from baseline (28-day baseline period) in the monthly average number of migraine days during the 12-week period after the first dose of IMP, will be analyzed using an analysis of covariance method. The model will include treatment, sex, puberty status, region, baseline weight category (<45.0 kg or  $\geq$ 45.0 kg), and preventive medication use at baseline (Yes/No) as fixed effects and baseline number of migraine days as a covariate. Ninety-five percent confidence intervals will be constructed for the least squares mean differences between the test IMP group and the placebo IMP group. A hierarchical procedure will be used to control Type 1 error rate, as described in Section 9.2.6.

##### **9.2.4.2. Sensitivity and Supplementary Analyses**

A sensitivity analysis for the primary efficacy endpoint will be conducted by using multiple imputation method for missing data. Sensitivity analysis using Mixed-Effect Model Repeated Measure method also will be conducted for change from baseline to months 1 through 3 in migraine days. A supplementary analysis using the ITT population will also be carried out for the primary efficacy endpoint. Additional subgroup analyses will be performed to investigate treatment effect among relevant sub-populations, such as sex, region, receiving preventive migraine therapy or not, receiving 2 preventive medications (Section 13.8), and receiving alternative preventive medications that belong to the same classes but are not listed in Section 13.8. The details will be described in the statistical analysis plan.

#### **9.2.5. Data Handling Conventions**

Efficacy variables from participants who do not have their diary completed for the entire trial period will be imputed. The detailed data imputation rules will be described in the statistical analysis plan.

##### **9.2.5.1. Handling of Withdrawals and Missing Data**

Efficacy variables based on diary data will be prorated to monthly rate. Sensitivity analysis for primary efficacy endpoint will be conducted using multiple imputation method for missing data.

### **9.2.6. Multiple Comparisons and Multiplicity**

A fixed-sequence (hierarchical) testing procedure will be implemented to control the Type 1 error rate at 0.05. The sequence of comparisons will start with the analysis of the primary endpoint and will follow with the secondary efficacy endpoints.

The order of secondary endpoint analyses will in general follow the sequence listed in Section 9.2.2. Final order and details will be confirmed in the statistical analysis plan, which will be finalized before database lock.

### **9.3. Analysis Supporting Secondary Objective(s)**

The same analysis used for the primary efficacy endpoint will be performed for the continuous secondary efficacy endpoints. For the proportion of responders, defined as at least 50% reduction from baseline in the monthly average number of migraine days, a logistic regression model will be used with the following factors: treatment, sex, region, puberty status, baseline weight category (<45.0 kg or  $\geq$ 45.0 kg), and preventive medication use at baseline (Yes/No). The odds ratio, 95% confidence interval for the odds ratio, and p-value for the treatment comparison will be presented.

### **9.4. Analysis of Exploratory Objective(s)**

### **9.5. Safety Analyses**

Safety analyses will be performed on the safety analysis set (Section 9.1.1).

Safety assessments and time points are provided in [Table 1](#).

All adverse events will be coded using the Medical Dictionary for Regulatory Activities. Each participant will be counted only once in each preferred term or system organ class category for the analyses of safety. Summaries will be presented for all adverse events (overall and by severity), adverse events determined by the Investigator to be related to test IMP (and/or PFS) (ie, reasonable possibility) (defined as related or with missing relationship) (overall and by severity), serious adverse events, serious adverse device effects, protocol-defined adverse events of special interest, adverse events, and adverse device effects causing withdrawal from the trial. Summaries will be presented by treatment group and for all participants. Participant listings of serious adverse events, serious adverse device effects, adverse events, and adverse device effects leading to withdrawal will be presented.

Changes in laboratory, ECG, and vital signs measurements data will be summarized descriptively. All values will be compared with predefined criteria to identify potentially clinically significant values or changes, and such values will be listed.

Suicidal ideation and behavior will be measured using the C-SSRS. Data for participants with positive findings will be listed.

The use of concomitant medications will be summarized by therapeutic class using descriptive statistics. Concomitant medications will include all medications taken while the participant is treated with IMP.

For continuous variables, descriptive statistics (n, mean, SD, median, minimum, and maximum) will be provided for actual values and changes from baseline to each time point. For categorical variables, participant counts and percentages will be provided. Descriptive summaries of serious adverse events, participant withdrawals due to adverse events, and potentially clinically significant abnormal values (clinical laboratory or vital signs) based on predefined criteria will be provided as well.

If any participant dies during the trial, a listing of deaths will be provided, and all relevant information will be discussed in the participant narrative included in the CSR.

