**Table 2: Investigational Medicinal Products Used in the Trial**

IMP name	Test IMP	Placebo IMP
Trade name and INN, if applicable, or company-assigned number	Fremanezumab	None
Formulation	Sterile, clear to opalescent, colorless to slightly yellow solution for injection	Sterile, clear to opalescent, colorless to slightly yellow solution for injection
Unit dose strength(s)/dosage level(s)	225 mg monthly in participants with body weight $\geq 45.0$ kg at randomization (visit 2) 120 mg monthly dose in participants with body weight $< 45.0$ kg at randomization (visit 2)	Not applicable
Route of administration	Subcutaneous injection	Subcutaneous injection
Dosing instructions	Participants with body weight $\geq 45.0$ kg at randomization (visit 2): fremanezumab 225 mg: 1 active injection (225 mg/1.5 mL) at visits 2, 3, and 4  Participants with body weight $< 45.0$ kg at randomization (visit 2): fremanezumab 120 mg: 1 active injection (120 mg/0.8 mL) at visits 2, 3, and 4	Participants with body weight $\geq 45.0$ kg at randomization (visit 2): Placebo: single 1.5-mL injection at visits 2, 3, and 4  Participants with body weight $< 45.0$ kg at randomization (visit 2): Placebo: single 0.8-mL injection at visits 2, 3, and 4
Intervention type	Drug	Placebo
Packaging	IMP will be provided as follows: 
 
225 mg dose: PFS for single-use administration
 
120 mg dose: taken from two 2-mL vials each containing 0.5 mL of IMP for single-use administration
 
	Placebo will be provided as follows: 
 
1.5-mL injection: PFS for single-use administration
 
0.8-mL injection: taken from two 2-mL vials each containing 0.5 mL of placebo for single-use administration
 

IMP name	Test IMP	Placebo IMP
Manufacturer	      	      

IMP=investigational medicinal product; INN=international nonproprietary name; PFS=pre-filled syringe.

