8. SAFETY ANALYSIS

8.1. General

The safety population will be used for all safety analyses. Summaries will be presented by treatment group (TEV-48125 225 mg, TEV-48125 120 mg and placebo). TEV-48125 will be presented as actually received unless specified otherwise. A total column will also be provided.

For continuous variables, descriptive statistics (n, mean, SD, median, minimum, and maximum) will be provided for actual values and changes from baseline to each time point. For categorical variables, participant counts and percentages will be provided.

Missing values will be reported as missing and no imputation will be undertaken.

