Listings for deaths, adverse events, adverse device effects, serious adverse events, serious adverse device effects, serious adverse events additional information, adverse events leading to discontinuation, adverse device effects leading to discontinuation, injection site related adverse event requiring concomitant or additional treatment given and protocol defined adverse events of special interest will be presented. All information pertaining to adverse events noted during the trial will be listed by subject, detailing verbatim given by the investigator, PT, SOC, date of onset, date of resolution, severity, and relationship to treatment. The onset of adverse events will also be shown relative (in number of days) to the 1st day of treatment. In addition, MedDRA dictionary terms for adverse event descriptions, and adverse event preferred terms by participant number and treatment group will be presented.

All adverse events summary tables will be split by the subgroups of 6-11 years, 12-17 years and overall.

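### Adverse device effect tables pool syringe-dosed and vial-dosed participants in the placebo and total columns, which dilutes those rates and distorts the comparison with 225 mg

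*Protocol*

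**What the plan says.** **Who is counted.** Protocol 9.5 runs safety analyses on the safety analysis set, and Protocol 9.1.1 defines it: "The safety analysis set will include all randomized participants who receive at least 1 dose of IMP". SAP 8.1 agrees: "The safety population will be used for all safety analyses".

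**How the tables are laid out.** The summaries planned in Protocol 9.5 include "serious adverse events, serious adverse device effects, protocol-defined adverse events of special interest, adverse events, and adverse device effects causing withdrawal from the trial". On columns, the same section says: "Summaries will be presented by treatment group and for all participants". SAP 8.1 is more specific: "Summaries will be presented by treatment group (TEV-48125 225 mg, TEV-48125 120 mg and placebo"), plus a total column. The SAP Introduction says the SAP prevails where the two differ. SAP 8.4 places treatment-emergent adverse device effects, serious adverse device effects and device effects leading to discontinuation in this by-treatment structure, and adds: "All adverse events summary tables will be split by the subgroups of 6-11 years, 12-17 years and overall".

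**Who uses the device.** Protocol Table 2 describes the lower dose as follows: "120 mg dose: taken from two 2-mL vials each containing 0.5 mL of IMP for single-use administration". The 0.8 mL placebo is packaged the same way. Protocol 6.6.1 and SAP 2.2 say that kits hold one pre-filled syringe for 225 mg and its placebo, or two vials for 120 mg and its placebo. Weight at randomization (45.0 kg or more, or less) fixes which presentation a participant gets. Protocol sections 8.4.2, 8.4.4 and 9.5 and Tables 3 and 5 refer to the pre-filled syringe as the device. No device is named for the vial presentation.

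**The concern.** A device-effect rate can be interpreted only among people who used the device. Neither document defines a syringe-exposed denominator. Participants under 45.0 kg in either arm have no planned syringe exposure, yet those on placebo count in the placebo column and all of them count in the total.

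The distortion has a direction. The SAP separates the active arm by dose, so the 225 mg column is all syringe users, but it leaves placebo pooled. A reader comparing the two would see a higher device-effect rate on 225 mg even if syringe users in both arms had the same risk. The placebo and total rates would also read too low as descriptions of syringe use. The effect should be stronger in the 6-11 table, where more participants are likely to weigh under 45.0 kg.

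**Working it through.** **Inputs from the documents.** 1:1 allocation (Protocol 4.1); 133 evaluable per group with 4% discontinuation, giving 139 per group and 278 in total (Protocol 9.8, SAP 2.4). The documents state neither a device-effect rate nor an expected share under 45.0 kg.

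**Plan's own figure.** 133 / 0.96 = 138.5, rounded up to 139 per group; 2 × 139 = 278. This reproduces and is used only as an approximate column size. SAP 15 removes one site from all analysis sets, so actual counts will differ.

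**Dilution.** Let p be the device-effect rate among syringe users and f the vial-dosed share of a column. If vial-dosed participants have no device effects, then:

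- displayed rate = p × (1 − f)
- 225 mg column: f = 0, so the displayed rate is p (barring dosing errors)
- 120 mg column: no planned syringe users
- placebo and total columns: displayed rate = p × (1 − f)
- ratio of 225 mg to placebo with equal p = 1 / (1 − f)

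**Numbers.** Two inputs are assumptions: f from 10% to 50%, and 5 syringe-related participants per arm for illustration. The planned placebo column is 5/139 = 3.6% throughout.

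| Assumed f | Vial / syringe users per arm | Placebo as planned | Placebo, syringe users only | 225 mg column | Spurious ratio |
|---|---|---|---|---|---|
| 10% | 14 / 125 | 3.6% | 5/125 = 4.0% | 4.0% | 1.11 |
| 20% | 28 / 111 | 3.6% | 5/111 = 4.5% | 4.5% | 1.25 |
| 30% | 42 / 97 | 3.6% | 5/97 = 5.2% | 5.2% | 1.43 |
| 40% | 56 / 83 | 3.6% | 5/83 = 6.0% | 6.0% | 1.67 |
| 50% | 70 / 69 | 3.6% | 5/69 = 7.2% | 7.2% | 2.01 |

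The total column behaves like placebo: 10/278 = 3.6% as planned, against 10/250 = 4.0% (f = 10%) to 10/138 = 7.2% (f = 50%) among syringe users. The last ratio is 2.01 rather than 2.00 because counts are whole participants. The ratio does not depend on the choice of 5 events.

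**Age tables.** The same formula holds with the age-specific f.

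**If the zero assumption fails.** If vial-dosed participants had a device-effect rate q, the placebo column would show p(1 − f) + qf. The distortion shrinks as q approaches p and disappears at q = p.

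**The case against.** Much of the case on the other side is sound, and it limits the point.

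- **The active rate is not understated.** A reader might infer that device-effect rates generally use every dosed child and are therefore too low. The SAP does not support that: its 225 mg column already contains only syringe users. Nor does it plan an all-fremanezumab column. The protocol's coarser wording would allow one, but the SAP prevails.
- **The 120 mg column is not certain to be zero.** The definition in Protocol 8.4.1.3 covers user error and events related to the procedures involved. Protocol Table 4 lists use errors such as faulty storage and missed inspection. The documents do not say what equipment is used to inject from vials. A zero is the natural expectation, not a certainty.
- **The 6-11 table need not mislead about young children.** The N of its 225 mg column would show how few of them used the active syringe.
- **The size is assumed.** Protocol 2 puts migraine prevalence under age 12 at less than one-third of that in adolescents, which favours the lower end of f overall.
- **The stakes are modest.** Device effects are not named among the safety endpoints, the device text came in with a template alignment, and no test or decision rule uses these tables. SAP 8.4 also lists every device effect by participant.

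What remains is that listings do not correct a tabulated percentage, and the pooled placebo and total columns still mix people who used the device with people who did not. Splitting placebo by presentation alone would repair the comparison with 225 mg but leave the total column diluted.

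**Conclusion.** The concern holds for the placebo and total columns, overall and by age group, and for the comparison of 225 mg with pooled placebo. Those rates are diluted by the factor (1 − f). With equal true rates the comparison shows a spurious ratio of 1/(1 − f), about 1.1 to 2.0 for an assumed f of 10% to 50%.

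This rests on three things: the pre-filled syringe is the only device, as the documents' wording indicates; vial-dosed participants have essentially no device effects; and the assumed range for f, which the documents do not give. The tables are descriptive, so the primary analysis and type I error are untouched. Severity is low.

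**What to change.** In SAP 8.4, and in Protocol 9.5 to match, state that all adverse device effect and serious adverse device effect summaries are computed among safety-set participants who actually received at least one dose by pre-filled syringe. Show 225 mg, syringe placebo and their total, and use the same denominator in the 6-11 and 12-17 tables.

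Define syringe exposure from the dosing CRF or kit type, not from weight at randomization. The safety set follows treatment actually received, and a participant given the wrong presentation would otherwise be misclassified. Keep any device-related event in a vial-dosed participant in the listings.

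The cost is one exposure flag, one sentence and slightly higher displayed rates. The note to file appended to the SAP says the trial analysis has been conducted. If the tables already exist, the corrected ones can be added and disclosed in the clinical study report, as Protocol 9 provides for additional or changed analyses.
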